#### 10. DATA

Will subjects be anonymous to the researcher? No

If subjects are identifiable, will their identities be kept confidential? (If yes, please specify how) Yes.

A copy of the consent form will be stored in a locked research cabinet or electronically on the lab server and REDCap within the University of Delaware Physical Therapy Department. Participant evaluations will be stored as part of their electronic medical record at the University of Delaware as required for insurance reimbursement.

Evaluations of individuals who agree to participate in the study will be coded (i.e. name at top of evaluation document will be replaced with participant ID number) and this coded evaluation will be stored electronically in a single Redcap project on the secure DRI server. Coded data will be stored indefinitely and will be accessible only to research personnel.

We will develop separate Redcap project on the secure DRI server that links participant ID numbers to participant names. This link will be destroyed three months after the conclusion of the study and will be accessible only to research personnel.

We will also develop a separate Redcap project on the secure DRI server that stores identifiable participant information. This information will be accessible only to research personnel. Identifiable participant information includes:

- Name
- Date of Birth
- Phone number(s)
- Email address
- Home address

To summarize, we will use three separate Redcap projects (all located on the secure DRI server). The first project will contain coded evaluation data (with participant ID numbers). The second project will contain a file that links participant ID numbers to participant names. The third project will contain identifiable participant information (including participant name and contact information).

How will data be stored and kept secure (specify data storage plans for both paper and electronic files. For guidance see http://www.udel.edu/research/preparing/datastorage.html )

See response above. To reiterate, we will secure informed consents in a locked file cabinet within the University of Delaware Physical Therapy Department that is accessible only to research personnel. We will store coded data and identifiable participant information electronically (using Redcap) on a secure DRI server.

How long will data be stored? Indefinitely

Will data be destroyed? 
VES X NO (if yes, please specify how the data will be destroyed)

Will the data be shared with anyone outside of the research team?  $\Box$  YES XNO (if yes, please list the person(s), organization(s) and/or institution(s) and specify plans for secure data transfer)

How will data be analyzed and reported?

Data will be coded and will be analyzed using appropriate statistical software packages. We will examine whether physical activity as measured by the Actigraph monitor is higher in those participants in the treatment versus Actigraph data from published studies. Results will be disseminated through written publications in reputable medical journals and professional presentations.

An interim analysis will be performed after half of the participant's 6 month follow-ups are completed. It is anticipated that this will be approximately 18 months after the start date. The interim analysis will be performed exactly the same as the final analysis. If the effect size of the physical activity intervention (which is standard care, a Fitbit™ monitor, individualized step goal, and face-to-face feedback with a physical therapist) group is greater than 3.0 (95% confidence interval 2.5-3.5), compared with the control group at this time point, then the intervention will have been deemed to work and the study will stop recruiting control group participants. Those in the control group currently will be asked if they want to switch arms and partake in the intervention.

At 18 months after the start of the study, we will conduct an interim analysis with four comparisons for adverse outcomes. The two arms of the study will be compared for number of AE, SAE, and UP, individually and jointly, if they are definitely or probably related to the intervention. If the intervention group is found to have more than 3.0 (95% confidence interval 2.5-3.5) times the odds of AE, SAE, UP, or their sum compared with the control, then we will stop the study.

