Exit Interview: After completing formal physical therapy rehabilitation, participants may be contacted via telephone by a researcher. The researcher will read several scripted exit interview questions to participants based on their group assignment. The information gathered from the exit interview will provide data on how to improve the feasibility of the study. See attached documents for exit interview questions.

Wawa or Amazon Gift Card: Participants will be given a \$25 gift card (i.e. Wawa, Amazon) at discharge from physical therapy rehabilitation. We will ask participants if they have gift card preference, if not we will give them Amazon gift card. We will continue the same gift card preference as stated by participant at discharge for 6-month and 12-month follow-up. They will be given a \$25 gift card for wearing the Actigraph at 6-months and a \$50 gift card for wearing it at 12-months.

**Control group:** The control group will receive standardized physical therapy rehabilitation, home exercise program, an Actigraph and exit interview.

**Intervention group:** The intervention group will receive standardized physical therapy rehabilitation, home exercise program, an Actigraph and exit interview. They will also receive the following:

Fitbit® monitor : Participants in the intervention group will be given a Fitbit® monitor after baseline physical activity data collection, approximately one week after enrollment. If a participant already has a physical activity monitor they can choose to use it instead of the Fitbit® monitor. However, they will still be given a Fitbit® monitor regardless if they already have a physical activity tracking device or not. They will be asked to wear their Fitbit® monitor daily during waking hours to monitor their steps per day. Participants will be given written instructions on how to sync their Fitbit® monitor to their personal smartphone, tablet, or home computer. A physical activity researcher will also explain how to set up, sync, and use Fitbit® monitor inperson. Extra batteries will be provided as needed. If the device is lost or damaged the participant will notify their physical therapist or the physical activity research team for a replacement. At the end of the 12-month follow up participants will be asked to return their Fitbit® monitor with their Actigraph via the mail. See attached documents for Fitbit® monitor Instructions.

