7.5.2 Planned Schedule of Interim Analyses

An interim analysis was performed after half of the participant's 6-month follow-up visits were completed.

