7.5.3 Scope of Adaptations and Stopping Rules

If the effect size of the intervention vs control exceeded 3.0 with a 95% CI of 2.5 to 3.5, then the intervention was to be deemed to be effective and study was to stop. As well, study participants who had not yet completed the intervention, i.e., were in physical therapy, and were in the control condition would have been offered the intervention. As well, we tallied the number of AEs, and compared that number between the intervention and control groups. If the intervention group was found to have more than three times the odds of AEs with a 95% CI of 2.5 to 3.5 compared with the control, then the study was to be stopped. Neither of

these events (efficacy or excessive AEs) occurred in the interim analyses.

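### The interim safety stopping criterion cannot be met as worded, the reading actually applied is not stated, and the fact that it was not triggered does not show absence of excess harm

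*Protocol*

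**What the plan says.** Protocol section 10 (DATA) announces the safety look: "At 18 months after the start of the study, we will conduct an interim analysis with four comparisons for adverse outcomes". The comparisons are of AEs, SAEs, UPs and their sum, counted "if they are definitely or probably related to the intervention". The study stops if the intervention group has "more than 3.0 (95% confidence interval 2.5-3.5) times the odds of AE, SAE, UP, or their sum compared with the control".

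SAP 7.5.3 gives the rule for AEs only, as "more than three times the odds of AEs with a 95% CI of 2.5 to 3.5 compared with the control", with no relatedness condition. It describes the comparison in the past tense: "we tallied the number of AEs, and compared that number between the intervention and control groups". It then reports that neither of "these events (efficacy or excessive AEs) occurred in the interim analyses".

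Neither document says whether the interval is a required result, a condition on the lower limit, or a loose description of the threshold. Neither gives the interval method, the handling of zero cells, the number at risk, or the interim counts or odds ratio.

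**The concern.** Read as written, the rule asks for a precision that no trial of this size can reach, so it would stay silent whatever the true harm. Greater harm does not help, because the upper limit then passes 3.5. If a looser reading was used, its meaning depends on which one, and that is not recorded.

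This is the only between-arm stopping criterion for harm in the documents, and Protocol section 8 says there is no external monitoring board. A reader of SAP 7.5.3 may well take the reported outcome as a safety check that was passed. What is at stake is how much that sentence can bear.

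**Working it through.** **Inputs.** Threshold 3.0 and 95% limits 2.5 and 3.5 (Protocol 10, SAP 7.5.3). Sample size 120 (SAP 7); target 130 and capacity 173 including the pilot (Protocol 7). The interim look came when half of the 6-month visits were complete (SAP 7.5.2), so about 60 participants, or 30 per arm, had 6-month data. The documents give no AE rate. Control risks of 5-30%, and separately 0.5-2%, are assumptions.

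**1. Does the rule agree with itself?** On the log scale an interval of 2.5 to 3.5 centres on √(2.5 × 3.5) = 2.96. On the plain scale it centres on 3.0. Neither is above 3.0.

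**2. Precision required.** SE(log OR) = ln(3.5/2.5)/(2 × 1.96) = 0.0858. With n per arm = [1/(p0q0) + 1/(p1q1)]/SE² at an odds ratio of 3:
- Most favourable risks (p0 = 0.366, p1 = 0.634): 8.619/0.0858² ≈ 1,170 per arm.
- p0 = 0.10 (p1 = 0.25): (11.11 + 5.33)/0.0858² ≈ 2,232 per arm.
- If the estimate must exceed 3.0 with an upper limit of at most 3.5: SE ≤ ln(3.5/3)/1.96 = 0.0786, so at least about 1,393 per arm.

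**3. What the trial could give.** All 2x2 tables without zero cells were enumerated, over every split with at least 5 per arm. None has its interval inside 2.5 to 3.5.

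| Total N | Narrowest upper/lower ratio | Ratio required |
|---|---|---|
| 60 | 7.57 | 1.40 |
| 120 | 4.18 | 1.40 |
| 130 | 3.96 | 1.40 |
| 173 | 3.29 | 1.40 |

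Tables with zero cells (0.5 added, equal arms) do not fit either. If events are counted instead of participants, SE² = (4/3)/(control events) at a ratio of 3. That needs 181 + 543 = 724 events, about 12 per participant with 60 participants.

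**4. Looser readings.** Exact binomial probability of triggering, one comparison, control risk 5-30%, 0.5 added when a cell is zero:

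| Reading | True OR | 30 per arm | 60 per arm |
|---|---|---|---|
| Point estimate above 3 | 1 | 3-23% | 0.4-15% |
| | 3 | 51-54% | 51-52% |
| | 5 | 74-83% | 81-91% |
| Lower limit above 2.5 | 3 | 0-4.5% | 0.3-6.7% |
| | 5 | 0.3-21% | 7.3-42.5% |

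At control risks of 0.5-2%, the point-estimate reading triggers 12-26% of the time with no excess (30 or 60 per arm).

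**5. What non-triggering tells us.** Take the ratio P(not triggered | OR 1)/P(not triggered | stated OR), for control risk 5-30%:
- Literal reading: 1.0 against any odds ratio.
- Lower limit: 1.0-1.07 against OR 3, 1.0-1.7 against OR 5.
- Point estimate: 1.7-2.0 against OR 3. Against OR 5, 2.95-5.62 at 30 per arm and 4.45-10.71 at 60. Against OR 10, about 15-66 at 30 per arm and 68 to over 900 at 60.

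With rarer events this weakens. At a control risk of 2% and 30 per arm, the point-estimate ratio against OR 5 is (1 − 0.255)/(1 − 0.700) = 2.48.

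**6. What was counted.** The protocol compares four related-event outcomes; the SAP compares AEs without a filter. The filter matters. "The control group will receive standardized physical therapy rehabilitation, home exercise program, an Actigraph and exit interview", so controls have no Fitbit or step goal and few of their events may qualify, although protocol section 10 also describes the intervention as including standard care. One event against none at 30 per arm already gives (1.5 × 30.5)/(29.5 × 0.5) = 3.10. The unit matters too, because the SAP tallies numbers while the rule is in odds. For illustration, 12 of 30 participants with 19 events against 6 of 30 with 6 events is an odds ratio of (12 × 24)/(18 × 6) = 2.67 but a count ratio of 19/6 = 3.17.

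**The case against.** The strongest reply is that the literal reading is the least plausible. The limits are symmetric about 3.0 on the plain scale, which an odds-ratio interval would not be, and both documents attach the same numbers to the efficacy effect size. The wording was probably loose. That is fair, and it means the defect is an undefined rule. A reader might infer that no working safety check took place. The documents do not support that: the looser readings can be met, and Protocol section 8 provides weekly AE review and reporting to the review board.

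A reader might also infer that non-triggering is worthless on every reading. It is not. On the point-estimate reading it argues against large harm, as step 5 shows.

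Thirty per arm is a low case, since SAP 6.4 collects AEs from the treatment period onward and participants without a 6-month visit also contribute. The 60-per-arm column covers this, and the conclusion is unchanged.

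Three further inferences should be resisted:
- **Timing.** The protocol's 18-month safety look is not in conflict with the SAP's trigger, "An interim analysis was performed after half of the participant's 6-month follow-up visits were completed". The protocol itself expects half of the 6-month visits at about 18 months.
- **Relatedness.** SAP 10.1 and 10.2 use other categories than the protocol's stopping rule, but for reporting. Different purposes need not share one set.
- **A claim of safety.** SAP 7.5.3 does not itself say there was no excess harm, and SAP 10 plans final safety tables by arm, so the final evidence does not rest on the interim sentence.

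**Conclusion.** The point holds, as something that should be fixed. The criterion is unattainable as worded at any size this trial could have had, by a wide margin and without any assumed event rate. The reading applied is unknown. The reported outcome is uninformative on the literal reading and nearly so against an odds ratio of 3 on the lower-limit reading. On the point-estimate reading it is evidence against odds ratios of 5 to 10 but only weak evidence against 3. On no reading does it show absence of excess harm.

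The sizes for the looser readings rest on the assumed control risks, 30 or 60 per arm, and a single comparison; the protocol's four comparisons are not modelled. Separately from the arithmetic, the protocol and SAP disagree on which events were compared.

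**What to change.** In SAP 7.5.3:
- Keep the historical rule on record and add that it was unattainable as worded at this sample size.
- State how it was applied: participants or events, which events and relatedness categories, which estimate or limit would have triggered action, the number at risk per arm, and the date of the look.
- Report the interim AE, SAE and UP counts by arm with the odds ratio and its interval, beside the final by-arm tables already planned in SAP 10. Do this after unblinding, so that the statistician's blinding under SAP 7.5.4 is kept.
- Do not cite non-triggering as evidence of no excess harm.

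Reconcile Protocol section 10 and SAP 7.5.3 on the events counted. As a separate item, reconcile the same two places on what an efficacy trigger leads to. The protocol stops control recruitment and asks current controls about switching; the SAP stops the study and offers the intervention to controls still in physical therapy.

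The cost is SAP wording and a little tabulation, with no new patients or data. The interim statement becomes less favourable. No new stopping rule is proposed.

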#### 11. CONFIDENTIALITY

Will participants be audiotaped, photographed or videotaped during this study? Yes

How will subject identity be protected?

The risk of breaching subject confidentiality will be minimized by identifying all participants by code numbers and by securing all data in locked files accessible only to research personnel. Neither the participant's name nor any identifying information will be used in any publication or presentation resulting from this study.

Is there a Certificate of Confidentiality in place for this project? (If so, please provide a copy).

No

12. CONFLICT OF INTEREST (For information on disclosure reporting see: http://www.udel.edu/research/preparing/conflict.html)

Do you have a current conflict of interest disclosure form on file through UD Web forms? Yes

Does this project involve a potential conflict of interest\*? No

\* As defined in the University of Delaware's Policies and Procedures, a potential conflict of interest (COI) occurs when there is a divergence between an individual's private interests and his or her professional obligations, such that an independent observer might reasonably question whether the individual's professional judgment, commitment, actions, or decisions could be influenced by considerations of personal gain, financial or otherwise.

If yes, please describe the nature of the interest: Not applicable

13. CONSENT and ASSENT

\_X\_\_\_ Consent forms will be used and are attached for review (see Consent Template under Forms and Templates in IRBNet)

\_ Additionally, child assent forms will be used and are attached.

\_\_\_X\_\_ Waiver of Documentation of Consent (attach a consent script/information sheet with the signature block removed).

We are requesting a Waiver of Documentation of Informed Consent in order to record and store eligibility information. The collection of the very basic eligibility criteria presents no more than minimal risk of harm to individuals and involves no procedures for which written informed consent is normally required. A verbal consent script is attached.

\_\_\_\_ Waiver of Consent (Justify request for waiver)

14. Other IRB Approval

Has this protocol been submitted to any other IRBs? No

If so, please list along with protocol title, number, and expiration date. Not applicable

15. Supporting Documentation

Please list all additional documents uploaded to IRBNet in support of this application.

- 1) Cover Letter
- 2) Amendment Form
- 3) CITI Training Certificates (HSP and GCP) for [name]

Rev. 09/2017

13	Listing of Tables, Listings and Figures	19

3 Abbreviations and Definitions

AE	Adverse Event
CRF	Case Report Form
SAP	Statistical Analysis Plan
PT	Physical Therapy
TKR	Total Knee Replacement
MVPA	Moderate to Vigorous intensity Physical
	Activity
UDPT	Delaware Physical Therapy Clinic at the
	University of Delaware

4 Introduction

4.1 Preface

Total Knee Replacement (TKR) is the most successful intervention to address pain from knee osteoarthritis. However, most resume a sedentary lifestyle gain weight and subsequently remain at high risk for poor health outcomes after surgery. There is a critical need for people after TKR to adopt an active lifestyle. Outpatient Physical therapy (PT) is an ideal, low-cost setting for a physical activity intervention for people after TKR given that physical therapists are experts at prescribing and personalizing exercises to meet patients' abilities over multiple outpatient visits. Unfortunately, little study has been devoted to the efficacy of a physical therapist delivered physical activity intervention. The objective of this paper is to evaluate the preliminary efficacy over 12 months of a physical therapist-delivered physical activity intervention at admission to PT. Next, the physical therapist provides face-to-face feedback on current activity levels and recommends step goals personalized to previous activity levels. The intervention is integrated into standardized outpatient PT for TKR.

4.2 Scope of the analyses

These analyses will assess the efficacy of standardized outpatient PT plus a Physical Therapist-administered physical activity intervention versus standardized outpatient PT alone with change in Moderate to Vigorous intensity Physical Activity (MVPA) over 6 months in adults after TKR.

5 Study Objectives and Endpoints

5.1 Study Objectives

The purpose of this study is to conduct a randomized, controlled trial to examine the effectiveness of a Physical Therapist-administered physical activity intervention in adults who received a TKR and sought care in an outpatient physical therapy (PT) clinic compared to outpatient PT alone.

5.2 Endpoints

The primary endpoint of our study is to examine the efficacy of a Physical Therapistadministered physical activity intervention and standardized outpatient PT to increase MVPA over 6 months after discharge from outpatient PT compared to a control group that received standardized outpatient PT.

The secondary analyses endpoint of our study is to examine the efficacy of a Physical Therapist-administered physical activity intervention and standardized outpatient PT to increase MVPA over 12 months after discharge from outpatient PT compared to a control group that received standardized outpatient PT. We will examine the number of steps/day over 6- and 12- months. Lastly, we will examine as an exploratory analysis to what extent baseline characteristics and treatment condition interact with study outcomes (MVPA and steps/day).

6 Study Methods

6.1 General Study Design and Plan

(ICH E3;9)

We conducted a pragmatic randomized controlled trial with a 2-group, superiority, paralleldesign. The intervention group received a Physical Therapist-administered physical activity intervention and standardized outpatient PT while the control group received standardized outpatient PT. The study was assessor-blinded, i.e., all members of the research team who were involved with the assessment of the primary and secondary outcomes were blinded. Study participants and treatment physical therapists were not blinded to group assignment. Figure: Study flow-chart

6.2 Inclusion-Exclusion Criteria and General Study Population

(ICH E3;9.3. ICH E9;2.2.1)

We recruited individuals who met the following inclusion criteria: 1) aged 45 years or older, 2) seeking outpatient physical therapist services for a unilateral TKR, and 3) were interested in increasing their PA. We excluded individuals who 1) had any comorbidities that made it unsafe for them to engage in PA, as instructed by a physician; 3) had a lower extremity surgery in the 6 months prior to study enrollment, or were planning a surgery in the 6 months after study enrollment; or 4) previously received a PA intervention at the Delaware Physical Therapy Clinic.

6.3 Randomization and Blinding

(ICH E3; 9.4.3, 9.4.6. ICH E9; 2.3.1, 2.3.2)

Participant-level randomization was performed to assign each participant to either the Intervention group or the Control group using a simple randomization schedule from the RAND() function in Microsoft Excel. Randomization occurred after participants provided signed informed consent to participate in the study and a research assistant determined they met study criteria. Randomization could have occurred after study participants started standardized outpatient PT.

A researcher not involved in recruitment or outcome assessment accessed the schedule, informed participants of their group assignment, and group assignment was concealed from the remaining members of the research team. This included blinding all members of the research team who were involved in the assessment of primary and secondary outcomes, or in statistical analysis of study outcomes. Participants and treating PTs were not blinded to their group assignment.

